## 2.4 Sample Size Determination

A total of 37 flares in the highest dose of ABBV-154 group and placebo group would provide more than 90% power to detect a hazard ratio of 0.296 at 2-sided significance level of 0.1. The hazard ratio of 0.296 is determined under the assumption that flares would occur during the tapering and within 12 weeks after the end of tapering (up to Week 36), and 70% and 30% of subjects will remain flare-free by Week 36 in the highest dose of ABBV-154 group and placebo group, respectively.

Based on an  $E_{\max}$  model with  $ED_{50}$  of 150 mg, a total of 74 flares are expected for the Primary Analysis. A sample size of 40 subjects in each of the ABBV-154 and placebo arms is planned to ensure appropriate accrual of flares. A sample size re-estimation may be considered at an interim analysis prior to unblinding of the study team. The sample size increase will be capped at approximately 100 subjects.

## 3.0 Endpoints

### 3.1 Primary Endpoint(s)

The primary endpoint is the time to flare, where flare is defined as follows:

- Presence of clinical signs and symptoms of PMR
- AND
- Requirement to increase the glucocorticoid dose per investigator.

Clinical signs and symptoms of PMR are defined as shoulder and/or hip girdle pain with inflammatory stiffness, neck pain with inflammatory stiffness, or new or worsened limited range of motion of hips and/or shoulders, as outlined in protocol.

### 3.2 Secondary Endpoint(s)

- Achievement of flare-free state up to Week 24
- Cumulative glucocorticoid dose by 24 weeks
- Change from Baseline in glucocorticoid dose at Week 24

### 3.3 Other Efficacy Endpoint(s)

The primary and/or secondary efficacy endpoints are listed in Section 3.1 and/or Section 3.2, respectively. All secondary endpoints will be analyzed at all visits other than those listed. In addition, the following endpoints will be analyzed at all visits assessed when applicable:

- Time to disease flare defined as Polymyalgia Rheumatica Activity Score (PMR-AS) increased from Baseline by  $\geq 6.6$ .
  - $\text{PMR-AS} = \text{high-sensitivity CRP (hsCRP) (mg/dL)} + \text{Patient Assessment of Pain Severity (numeric rating scale [NRS], 0 - 10)} + \text{Physician Global Assessment of Disease Activity (NRS, 0 - 10)} + (\text{morning stiffness duration [MST] in minutes} \times 0.1) + \text{elevation of upper limbs (EUL) (scale of 3 - 0)}$
- Time to disease flare defined as  $\text{PMR-AS} \geq 9.35$
- Achievement of  $\text{PMR-AS} < 1.5$
- Achievement of  $\text{PMR-AS} < 7$
- Achievement of  $\text{ESR} \leq 30 \text{ mm/h}$  at Week 24
- Achievement of  $\text{hsCRP} \leq \text{upper limit of normal (ULN)}$  at Week 24
- Change from Baseline in hsCRP
- Change from Baseline in PMR-AS
- Change from Baseline in MST
- Change from Baseline in EUL
- Change from Baseline in Physician Global Assessment of Disease Activity NRS
- Change from Baseline in Patient Assessment of Pain Severity NRS
- Change from Baseline in Patient Assessment of Stiffness Severity NRS
- Change from Baseline in Functional Assessment of Chronic Illness Therapy-Fatigue (FACIT-Fatigue)
- Change from Baseline in Health Assessment Questionnaire Disability Index (HAQ-DI)

- Change from Baseline in Patient-Reported Outcomes Measurement Information System (PROMIS) Item Bank v 1.0 – Sleep Disturbance
- Change from Baseline in Patient Assessment of Bruising Severity NRS
- Change from Baseline in EuroQol 5-dimension questionnaire, 5-level (EQ-5D-5L)
- Change from Baseline in Physician Assessment of Bruising Severity NRS
- For subjects participating in the Wearable Device Substudy:
  - Change from Baseline in the following sleep parameters: total sleep time, wake after sleep onset, sleep efficiency, and sleep onset latency
  - Change from Baseline in upper limbs range of motion (UL-ROM)

### **3.4 Safety Endpoint(s)**

Safety measures monitored in the study include the following:

- Treatment-emergent adverse events (TEAEs), serious adverse events (SAEs), and AEs leading to discontinuation of study drug;
- Occurrence of potentially glucocorticoid-related AEs; and
- Potentially clinically significant laboratory, vital signs, and electrocardiogram (ECG) variables.

### **3.5 Additional Endpoint(s)**

Pharmacokinetic, immunogenicity, and biomarker research endpoints will be analyzed separately, and the corresponding analysis plan is not covered in this SAP.

## **4.0 Analysis Populations**

The following population will be used for the efficacy analysis except for Wearable Device Substudy-related endpoints:

- Intent-to-Treat (ITT) Population: The ITT Population includes all subjects who were randomized and received at least 1 dose of study drug. The ITT

Population will be analyzed as randomized (i.e., according to the randomized treatment assignment).

The following population will be used for the safety analysis:

- Safety Population: The Safety Population includes all subjects who were randomized and received at least 1 dose of study drug. The Safety Population will be analyzed as treated (i.e., according to the actual treatment received).

The Per-Protocol Population will include ITT subjects with the exception of those who have major protocol deviations that are determined to have a potential impact on the primary efficacy endpoint up to Week 24. The final criteria and the exclusion of subjects for the per-protocol population will be finalized before unblinding data for the Primary Analysis.

## **5.0 Subject Disposition**

The total number of subjects who were screened, enrolled (randomized), and treated will be summarized. Reasons for exclusion, including screen failure, will be summarized.

A summary of subject accountability will be provided where the number of subjects in each of the following categories will be summarized for each treatment group:

- Subjects enrolled (randomized) in the study;
- Subjects who took at least one dose of study drug;
- Subjects who completed protocol-specified treatment;
- Subjects who prematurely discontinued study drug (all reasons and primary reason);
- Subjects in each analysis population, as applicable.

For end of study participation, the number and percentage of subjects who completed the protocol defined follow-up period (or did not with associated reasons) will be summarized overall and by treatment group.

## **6.0 Study Drug Duration and Compliance**

For the Safety population, duration of treatment will be summarized for each treatment group and for all investigational study drug dose groups combined. Duration of treatment is defined for each subject as last dose date minus first dose date plus 14 days. Duration of treatment will be summarized using the number of subjects treated, mean, standard deviation, median, minimum and maximum. In addition, the number and percentage of subjects in each treatment duration interval (< 2 weeks [14 days], ≥ 2 weeks [14 days], ≥ 4 weeks [28 days], ≥ 8 weeks [56 days], ≥ 12 weeks [84 days], ≥ 24 weeks [168 days], ≥ 36 weeks [252 days], and ≥ 52 weeks [364 days]) will be summarized.

Treatment compliance will be summarized for the entire treatment period by treatment group and total ABBV-154 group for the Safety population. Treatment compliance is defined as the number of injection actually taken divided by the number of injection that should have been taken. All placebo injections will be included in the calculation for treatment compliance. Percent compliance will be summarized.

## **7.0 Demographics, Baseline Characteristics, Medical History, and Prior/Concomitant Medications**

Demographics, baseline or disease characteristics, medical history, and prior and concomitant medications will be summarized for the ITT overall and by treatment group. Categorical variables will be summarized with the number and percentage of subjects; percentages will be calculated based on the number of non-missing observations. Continuous variables will be summarized with descriptive statistics (number of non-missing observations, mean and standard deviation, median, minimum and maximum).

### **7.1 Demographics and Baseline Characteristics**

Continuous demographic variables include age, weight, height, and body mass index (BMI). Categorical demographic variables include sex, ethnicity, race, age Group 1 (< 65, or ≥ 65 years), age Group 2 (< 65, ≥ 65 and < 75, or ≥ 75 years), weight Group 1

(< 60 or ≥ 60 kg), weight Group 2 (< 100 or ≥ 100 kg), BMI Group 1 (< 25 or ≥ 25 kg/m^2), BMI Group 2 (< 35 or ≥ 35 kg/m^2), region (Europe, North America, or rest of world), tobacco user (current, former, never, unknown), and alcohol user (current, former, never, unknown).

Disease characteristics that will be summarized as continuous and categorical variables are listed below:

### **PMR Medical History and Characteristics**

- Duration of PMR diagnosis in years
- Duration of PMR diagnosis category (< 1, ≥ 1 and ≤ 2, or > 2 years)

### **Baseline PMR Disease Characteristics**

- High sensitivity c-reactive protein (hs-CRP) (mg/L)
- Erythrocyte sedimentation rate (ESR) (mm/h)
- Patient Assessment of Pain Severity Numeric Rating Scale (NRS)
- Physician Global Assessment of Disease Activity NRS
- Morning Stiffness (MST) Duration
- Elevation of Upper Limbs (EUL)
- Polymyalgia Rheumatica Activity Score (PMR-AS)
- Polymyalgia Rheumatica Activity Score (PMR-AS) (< 1.5, ≥ 1.5 and < 7, ≥ 7 and < 17, or ≥ 17)
- Patient Assessment of Stiffness Severity NRS
- Functional Assessment of Chronic Illness Therapy-Fatigue (FACIT-Fatigue)
- Health Assessment Questionnaire Disability Index (HAQ-DI)
- Patient-Reported Outcomes Measurement Information System (PROMIS) – Sleep Disturbance
- Patient Assessment of Bruising Severity NRS
- EuroQol 5-dimension questionnaire, 5-level (EQ-5D-5L)
- Physician Assessment of Bruising Severity NRS

- Rheumatoid factor (Positive ( $\geq 14$  IU/mL), Negative ( $< 14$  IU/mL))
- Time since most recent PMR flare prior to Baseline ( $\leq 12$  weeks,  $> 12$  weeks)

### **Prior and Concomitant Treatment use**

- Length of prior glucocorticoid treatment for PMR\* category ( $\leq 1$  or  $> 1$  year)
- Baseline glucocorticoid dose
- Baseline glucocorticoid dose categories 1 ( $< 10$  or  $\geq 10$  mg/day prednisone equivalent)
- Baseline glucocorticoid dose categories 2 ( $< 7.5$ ,  $\geq 7.5$  and  $< 10$ ,  $\geq 10$  and  $\leq 15$ , or  $> 15$  mg/day prednisone equivalent)
- Prior biologic DMARD use (yes/no)
- Prior synthetic DMARD use (yes/no)
  - Prior conventional synthetic DMARD use (yes/no)
  - Prior targeted synthetic DMARD use (yes/no)
- Length of prior glucocorticoid use for PMR\* (years)
- Prior cumulative glucocorticoid dose (mg)
- Prior cumulative glucocorticoid dose (mg) (within one year before randomization)

\*: Only consider glucocorticoid treatment use on or after confirmed PMR diagnosis date

## **7.2 Medical History**

Medical history data will be coded using the Medical Dictionary for Regulatory Activities (MedDRA). The actual version of the MedDRA coding dictionary will be noted in the statistical tables and clinical study report. The number and percentage of subjects in each medical history category (by MedDRA system organ class and preferred term) will be summarized overall and by treatment group. The system organ class (SOC) will be presented in alphabetical order, and the preferred terms will be presented in alphabetical

order within each SOC. Subjects reporting more than one condition/diagnosis will be counted only once in each row (SOC or preferred term).

### **7.3 Prior and Concomitant Medications**

Prior and concomitant medications will be summarized by generic name. A prior medication is defined as any medication taken prior to the date of the first dose of study drug. A concomitant medication is defined as any medication that started prior to the date of the first dose of study drug and continued to be taken after the first dose of study drug or any medication that started on or after the date of the first dose of study drug, but not after the date of the last dose of study drug plus 70 days. The number and percentage of subjects taking medications will be summarized by generic drug name based on the World Health Organization (WHO) Drug Dictionary for both prior and concomitant medications.

### **8.0 Handling of Potential Intercurrent Events for the Primary and Secondary Endpoints**

The primary efficacy endpoint (defined in Section 3.1) will be analyzed based on the ITT population and subjects will be censored at the time of the last available assessment, initiation of immunomodulator, or violation of protocol-allowed systemic glucocorticoid use.

The categorical secondary efficacy endpoint (defined in Section 3.2) will be analyzed based on the ITT population and the following methods will be used to address the potential intercurrent events:

- Subjects will be considered as not achieving the response after the initiation of rescue medication, immunomodulator or violation of protocol-allowed systemic glucocorticoid use.

The continuous secondary efficacy endpoints (defined in Section 3.2) will be analyzed based on the ITT population and the following methods will be used to address the potential intercurrent events:

- No intercurrent event will be considered in the analysis of glucocorticoid dose.

## **9.0 Efficacy Analyses**

### **9.1 General Considerations**

All efficacy analyses will be conducted in the ITT Population in each period. In addition, Per-protocol analysis for the primary endpoint will be performed. All tests will be 2-sided at an alpha level of 0.1.

The Primary Analysis will be performed after all subjects have either completed the Week 24 visit or withdrawn from the study. This analysis will be the only and final analysis for the primary and secondary efficacy endpoints.

The primary endpoint will be analyzed using logrank test stratified by baseline stratification factors [Glucocorticoid use at Baseline ( $\geq 10$  mg/day;  $< 10$  mg/day prednisone equivalent); Length of prior glucocorticoid treatment for PMR ( $\leq 1$  year;  $> 1$  year)]. The point and 95% confidence interval (CI) estimate of median time to event and event-free rate for each group will be reported based on Kaplan-Meier curves. Hazard ratio and its corresponding 95% CI for each ABBV-154 group compared with placebo will be estimated using Cox regression analysis adjusting for Baseline stratification factors [Glucocorticoid use at Baseline ( $\geq 10$  mg/day;  $< 10$  mg/day prednisone equivalent); Length of prior glucocorticoid treatment for PMR ( $\leq 1$  year;  $> 1$  year)]. For all analyses of time-to-event endpoints, 1) subject without an event at the time of the analysis will be administratively censored at the time of the last available assessment or cutoff, whichever is later; 2) a flare at Baseline will not be counted as an event; 3) if a flare event and an intercurrent event happen on the same day, subject will be counted as having a flare event.

Unless otherwise specified, the categorical endpoints and continuous endpoints will be analyzed by Cochran-Mantel-Haenszel (CMH) and Mixed-Effect Model Repeat

Measurement (MMRM), respectively, and the corresponding analyses are specified in Section 9.2.

Unless otherwise specified, any subject who is randomized based on a wrong stratum will be analyzed according to the actual stratum the subject belongs to.

"Baseline" refers to the last non-missing observation on or before the day of the first administration of study drug or randomization if no study drug is given. Observation on the same day as the first administration of study drug will be considered for the baseline, regardless of whether observation time (if available) was before or after the first administration of study drug time.

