APPENDIX G. PROTOCOL SUMMARY OF CHANGES

Previous Protocol Versions

Protocol	Date
Version 1.0	13 May 2021
Version 2.0	13 July 2021
Version 2.1 (UK only)	29 September 2021
Version 2.2 (France only)	19 October 2021
Version 2.3 (Germany only)	23 November 2021

The purpose of this version is to update the following sections below. In addition, minor typographical edits have been made for consistency throughout the Protocol and Operations Manual.

Summary of Protocol Changes:

- Protocol Section 1, Synopsis; Protocol Section 4.1, Overall Study Design and Plan including Figure 1, Section 5.9, Randomization/Drug Assignment; Section 7.10, Sample Size Determination; Operations Manual, Section 6.3, Method of Assigning Subjects to Treatment Groups: Changed the randomization ratio from 2:1:1:1 to 1:1:1:1 and the total subjects to be enrolled from 200 to 160.

Rationale: To reduce the proportion of placebo subjects to match the number of subjects in each ABBV-154 dose group. Reduction in the number of placebo patients maintains the power for the primary endpoint.
- Protocol Section 1, Synopsis, Investigational Plan: Follow-up "Visit" changed to Follow-up "Period."

Rationale: To reflect the duration of follow-up, as the follow-up period is now comprised of a follow-up phone call and a follow-up visit as opposed to a single visit.
- Protocol Section 1, Synopsis, Investigational Plan; Protocol Section 4.1, Overall Study Design and Plan and Operations Manual Section 3.9, Wearable Device Substudy: Changed the enrollment cap for the Wearable Device Substudy from 120 to 96.

Rationale: To align with the change in the randomization ratio and the reduction of number of subjects in the placebo arm.
- Protocol Section 1, Synopsis, Key Eligibility Criteria; Protocol Section 4.2, Discussion of Study Design and Section 5.1, Eligibility Criteria: Deleted upper age limit of 80 (criterion #2).

Rationale: To align the study population with the known epidemiology of PMR.
- Protocol Section 1, Synopsis, Investigational Plan; Protocol Section 5.1, Eligibility Criteria: Deleted dosage specifications for clinical response to prednisone or equivalent from criterion #7.

Rationale: To align with 2015 EULAR/ACR treatment recommendations and real-world practice, which may include intramuscular injections of glucocorticoid with initial higher doses > 25 mg/d prednisone equivalent.

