- Protocol Section 3.6, Pharmacokinetic and Immunogenicity Endpoints: Changed the number of subjects needed for collecting the optional PK samples from approximately 40 to approximately 32 subjects (approximately 8 subjects in each arm).

Rationale: To align with the change in the randomization ratio and the reduction of number of subjects in the placebo arm.

- Protocol Section 4.1, Overall Study Design and Plan and Operations Manual, Section 3.9 Wearable Device Substudy: Removed requirement to participate in the Wearable Device Substudy as a condition for overall study participation in subjects who otherwise qualify for the Substudy.

Rationale: To allow subjects the option to participate in the main study in the case they do not choose to participate in the Wearable Device Substudy.

- Protocol Section 4.1, Overall Study Design and Plan and Figure 1, and Section 7.8, Interim Analysis: Modified plan for Interim analyses.

Rationale: To reduce the number of planned interim analyses to reassess the treatment regimens in this study and to inform the development of future studies and allow flexibility in interim analysis timing to account for variability in the observed enrollment rate.

- Protocol Section 5.1, Eligibility Criteria: Updated history of GCA to specify a diagnosis may be based on clinical, ultrasound, and/or temporal artery biopsy.

Rationale: To clarify the definition of history of GCA considered exclusionary for this study, for which diagnosis may be established clinically, or by ultrasound and/or temporal artery biopsy even if clinical symptoms of GCA were not present.

- Protocol Section 5.1, Eligibility Criteria: Changed criterion #14 to exclude active fibromyalgia.

Rationale: To allow subjects with inactive fibromyalgia to participate in the study, as inactive fibromyalgia is not considered a confounder and will not affect subject safety.

- Protocol Section 5.1, Eligibility Criteria: Moved wording in criterion #14 regarding inflammatory arthritis to a new bullet and added wording to allow subjects with stable gout to participate in the study.

Rationale: The bullet was reorganized to address inflammatory arthritis in a separate point from other rheumatic diseases excluded. To allow subjects with stable gout to participate in the study, as stable gout controlled on suppressive therapy and without recent flare is not expected to interfere with interpretation of PMR flare and will not affect subject safety.

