- Protocol Section [7.10](#), Sample Size Determination: Changed the total number of flares from 64 to 37 for the highest dose and placebo arms and from 101 to 74 for all treatment arms combined.

Rationale: The expected total number of flares is reduced as the result of changing the randomization ratio and sample size.
- Protocol Section [7.10](#), Sample Size Determination: Revised the timing of the possible sample size re-estimation to be at one interim analysis to occur prior to unblinding of the study team.

Rationale: To align with modifications to remove specific timing and number of planned interim analyses and clarify that sample size re-estimation will occur before the study team is unblinded.
- Protocol [Appendix A](#), Study Specific Abbreviations and Terms: Corrected the terms for hepatitis surface antibody abbreviation.

Rationale: To correct a typographical error.
- Protocol [Appendix C](#), List of Protocol Signatories: Updated list of protocol signatories.

Rationale: Administrative change.
- Protocol [Appendix F](#), Activity Schedule: Added additional column for the 30-day follow-up phone call to assess adverse events and prior/concomitant therapy and added "Visit" to 70-day follow-up column header.

Rationale: Added a 30-day follow-up call and clarified that the 70-day follow-up is a visit to ensure all treatment-emergent AEs/SAE have been resolved.
- Protocol [Appendix F](#), Activity Schedule (including footnote c); Operations Manual, Section 2.1 Individual Treatment Period Visit Activities (footnotes); Operations Manual, Section 3.9 Wearable Device Substudy: Reduced the duration of time during which subjects participating in the Wearable Device Substudy wear the device.

Rationale: To limit data collection for this substudy to the one week after site visits at which UL-ROM is performed to reduce subject burden and increase subject compliance to substudy procedures.

- Protocol [Appendix F](#), Activity Schedule; Operations Manual Section 2.4, Individual Post-Treatment Period Visit Activities: Added body weight and vital signs collection to 70-day follow-up visit.

Rationale: To ensure more robust safety data collection at follow up.
- Protocol [Appendix F](#), Activity Schedule; Operations Manual Section 2.1 Individual Treatment Period Visit Activities and Section 3.19, Clinical Laboratory Tests, Table 1: Added collection of 25-hydroxyvitamin D to the Baseline Visit and to Table 1, Clinical Laboratory Tests.

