Rationale: To collect additional data on subjects Baseline status which may affect bone mineral density.
- Protocol [Appendix F](#), Activity Schedule; Operations Manual Section 2.4, Individual Post-Treatment Period Visit Activities: Added PK and immunogenicity sample collection at the 70-day Follow-Up Visit.

Rationale: To ensure drug washout and assess immunogenicity during drug washout.
- Operations Manual, Section 1, Contacts: Updated Clinical Lab and Biomarker Sample Storage contact information.

Rationale: Administrative change.
- Operations Manual, Section 2.1, Individual Treatment Period Visit Activities: All individual study day headers were updated to include an additional column.

Rationale: Added for alignment with the 30-day phone call column in the Study Activity Table.
- Operations Manual, Section 2.1, Individual Treatment Period Visit Activities: For screening visit, changed reference for Section 3.6 to 3.5, describing chest x-ray.

Rationale: To correct typographical error.
- Operations Manual, Section 2.2 Premature Discontinuation Visit, Footnote b: Footnote was removed.

Rationale: Footnote was not applicable to the premature discontinuation visit anymore since subjects no longer wear the device continuously.
- Operations Manual Section 3.2, Rescreening: Added additional opportunity for rescreening of subjects with the AbbVie Therapeutic Area Medical Director/Scientific Director approval.

Rationale: To allow subjects who have already been screened twice the opportunity to rescreen on a case-by-case basis, if appropriate.
- Operations Manual Section 3.2, Rescreening: Added FSH to the list of testing not required to be repeated if rescreening a subject within 14 days from the sample collection date of the previous screen.

Rationale: To reduce unnecessary procedures, as FSH would not be expected to change significantly in 14 days.
- Operations Manual Section 3.6, Dual-Energy X-Ray Absorptiometry (DXA) Scan: Added collection of Z-score for evaluation of bone mineral density and instruction that measurements should be obtained from the distal forearm if the spine nor either hip are able to be scanned or

interpreted. Added a Central Imaging Core Lab for central independent review of DXA data and modified guidance for image acquisition.

Rationale: To improve the robustness and interpretability of the DXA data collected.

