#### **9.4.2 Main Analyses of Secondary Efficacy Endpoints**

The statistical null hypothesis corresponding to the secondary endpoint is that there is no difference between an ABBV-154 group and the placebo group.

Analysis of the secondary endpoint will be conducted in the ITT Population based on treatment as randomized. Comparison of the secondary endpoint will be made between each ABBV-154 group and the placebo group using:

- For categorical variable: CMH test adjusted by baseline randomization stratification factor [Glucocorticoid use at Baseline ( $\geq 10$  mg/day;  $< 10$  mg/day prednisone equivalent); Length of prior glucocorticoid treatment for PMR ( $\leq 1$  year;  $> 1$  year)].
- For analyses of glucocorticoid dose: ANCOVA mentioned in Section 9.2.

The attributes of the estimands corresponding to the secondary efficacy endpoints are summarized in Table 2.

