## 14.0 Version History

**Table 5. SAP Version History Summary**

Version	Date	Summary
1.0	29 November 2021	Original version
2.0	03 August 2022	
 
• Section 2.2, Section 2.3, Section 2.4, and Section 12.0: update the sample size, interim analysis language, sample size for Wearable Device Substudy, study schematics, randomization ratio, to align with protocol version 3.0.
 
• Section 7.1: update/add details for the age Group 1, Rheumatoid factor, and length of prior glucocorticoid use for PMR, add summarization for time since most recent PMR flare prior Baseline (<math>\leq</math> 12 weeks, <math>></math> 12 weeks).
 
• Section 9.1: add details for time-to-event (censoring, event at the Baseline, event and flare happen on the same day) and efficacy Baseline definition.
 
• Section 9.2: add statements for NRI instead of NRI-MI will be used in the interim analysis.
 
• Section 9.5: clarify the intercurrent event for the additional efficacy endpoint.
 
• Section 9.7: add efficacy subgroup time since most recent PMR flare prior Baseline (<math>\leq</math> 12 weeks, <math>></math> 12 weeks)
 
• Section 10.1: add details for safety Baseline definition
 
• Section 10.2: clarify the definition of Treatment-emergent AEs; use AESI instead of STI for terminology
 
• Section 10.5: add new safety subgroup
 
• Section 10.6: add details for BMD analysis
 
• Appendix B: add PCI criteria for selected laboratory variables.
 

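### Allocation changed from 2:1:1:1 to 1:1:1:1 at protocol version 3.0, but no efficacy analysis conditions on allocation schedule; if both schedules enrolled subjects, the placebo contrasts may be modestly biased

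*SAP*

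**What the plan says.** Protocol Appendix G records the change: "Changed the randomization ratio from 2:1:1:1 to 1:1:1:1 and the total subjects to be enrolled from 200 to 160". It is used here only as a record of how the trial was run; its difference from the current text is not the point. The SAP version history shows that SAP version 2.0 (3 August 2022) was revised for the new "randomization ratio, to align with protocol version 3.0".

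Appendix G lists eligibility changes in the same amendment. The upper age limit of 80 was removed and the dose specification for prior prednisone response was dropped. Stable hydroxychloroquine, stable gout, inactive fibromyalgia and malignancy more than 5 years ago became acceptable.

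On the analysis, SAP 9.1 says: "The primary endpoint will be analyzed using logrank test stratified by baseline stratification factors". The factors listed are baseline glucocorticoid dose (≥ 10 or < 10 mg/day) and length of prior glucocorticoid treatment (≤ 1 or > 1 year). The Cox model uses the same pair. SAP 9.4.2 specifies, for the binary secondary endpoint, a "CMH test adjusted by baseline randomization stratification factor", with the same pair again. The MMRM and ANCOVA in SAP 9.2.2 add only baseline value and, for MMRM, visit terms. Allocation schedule, protocol version and enrolment period appear in no model and in no subgroup (SAP 9.7). SAP 9.3.3 and 9.4.3 plan no sensitivity analyses.

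**The concern.** Randomization makes arms comparable within one allocation schedule. When two schedules with different ratios are pooled and the analysis ignores which one a subject came from, the arms differ in their mix of early and late subjects. Under 2:1:1:1, 40% of subjects go to placebo and 20% to each dose; under 1:1:1:1, 25% go to each arm. Placebo is therefore weighted towards the early period.

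If flare risk differs between periods, part of that difference enters every dose-versus-placebo hazard ratio, flare-free difference and glucocorticoid-dose difference. The direction is the same for all three doses because they share one placebo arm. The eligibility changes give a reason why risk might differ. What is at stake is mainly the weaker contrasts (lower doses) and the dose-response model in SAP 9.6, which works from summary response rates that include placebo.

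**Working it through.** **The plan's own figures (Protocol 7.10, SAP 2.4).** Flare-free rates at Week 36 are 70% (highest dose) and 30% (placebo). HR = ln(0.70)/ln(0.30) = 0.296, as stated. Power with 37 flares, 1:1, two-sided 0.1 (Schoenfeld): √(37 × 0.25) × |ln 0.296| − 1.645 = 3.703 − 1.645 = 2.058, which is 98.0%. The Freedman form gives 95.1%. Both agree with the stated figure of more than 90%.

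**Imbalance in period.** N0, the number randomized at 2:1:1:1, is not given, so it is assumed. With 160 subjects in total:

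- Placebo early share = 0.4·N0 / [0.4·N0 + (160 − N0)/4]
- Each dose's early share = 0.2·N0 / [0.2·N0 + (160 − N0)/4]

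| N0 | Placebo | Each dose | Gap in early share | Spurious difference if flare-free rates differ by 20 points between periods (assumed) |
|---|---|---|---|---|
| 20 | 8/43 = 19% | 4/39 = 10% | 8.3 points | 1.7 points |
| 40 | 16/46 = 35% | 8/38 = 21% | 13.7 points | 2.7 points |
| 60 | 24/49 = 49% | 12/37 = 32% | 16.5 points | 3.3 points |

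**Effect on the log-rank comparison when the true HR is 1.** Simulation of placebo against one dose: exponential flare times, 30% flare-free at Week 36 in the early period, follow-up of 52 weeks for early and 24 to 52 weeks for late subjects, other strata ignored, 4,000 runs per setting. Here g is the flare hazard in the late period relative to the early one (assumed). Each cell gives the estimated HR and the one-sided rejection rate favouring drug (nominal 5%).

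| g | 25% early, schedule ignored | 50% early, schedule ignored |
|---|---|---|
| 0.5 | 0.903; 9.0% | 0.895; 10.3% |
| 0.67 | 0.952; 6.6% | 0.943; 7.2% |
| 1 | 1.004; 4.8% | 1.010; 5.0% |
| 1.5 | 1.066; 2.6% | 1.077; 2.6% |
| 2 | 1.105; 1.8% | 1.119; 1.4% |

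Stratifying by schedule gives an HR of 1.00 to 1.01 and 4.4% to 5.4% in every setting. A hand check: the bias in log HR is roughly the gap in early share times ln(g). For 25% early and g = 0.5, that is 0.137 × (−0.693) = −0.095, so an HR of about 0.91, close to the simulated 0.903. Two-sided rejection without schedule is 9.2% to 13.2% against 10%; it moves less because the two tails partly offset.

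**At the design effect.** With a true HR of 0.296, g from 0.67 to 1.5 and 2,000 runs per setting, power is at least 97% with or without schedule.

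**At the lowest dose.** Applying the Emax assumption (ED50 150 mg) to the flare-free rate, the 40 mg gain over placebo is 40 points × (40/190)/(340/490) = 12.1 points. The spurious 1.7 to 3.3 points is 14% to 27% of that. Against the 22% target for the minimum effective dose in SAP 9.6 it is 8% to 15%.

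**The case against.** The strongest reply is that the premise is not documented. No section says that anyone was randomized at 2:1:1:1. The evidence is indirect: global versions dated May and July 2021, country versions from September to November 2021, a current synopsis dated 21 February 2022, and a rationale for changing the interim analyses that includes the wish to "allow flexibility in interim analysis timing to account for variability in the observed enrollment rate". Both documents plan 40 per arm, which may mean that few early subjects were expected. The Operations Manual section on assigning subjects to treatment was also changed but is not available. This stands, and it makes the point conditional. The 40-per-arm target does not remove it, though. With 40 early subjects, the stated ratios give 46 placebo and 38 per dose. If the arms were instead brought to 40 each, the early shares would be 16/40 v 8/40, a gap of 20 points rather than 13.7.

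The second reply is size. A 20-point difference between periods has no source. Suppose 20% of late subjects were newly eligible and had half the flare hazard (assumed). Their flare-free rate would be √0.30 = 55% instead of 30%, the period difference about 5 points, and the spurious arm difference with 40 early subjects about 0.7 points. This also stands: eligibility alone probably puts the bias at the low end.

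Three stronger readings are tempting and should be resisted.

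- That the analyses are unstratified. They use two baseline factors; only schedule is missing.
- That the amendment changed how flare is ascertained. Entries such as "Added collection of 25-hydroxyvitamin D to the Baseline Visit" and "Added a Central Imaging Core Lab for central independent review of DXA data and modified guidance for image acquisition", the shorter wearable time and the 30-day call have no role in flare or glucocorticoid dose, and the flare definition is not listed as changed.
- That period and placebo are fully confounded. The imbalance is partial.

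**Conclusion.** The omission is real and is in the current SAP, which was revised for the new ratio without extending the models. Whether it causes bias depends on two things the documents do not establish: that subjects were randomized at 2:1:1:1, and that flare risk differs between the two periods. If either is false, there is no bias.

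If both are true, the bias is modest: a null HR of about 0.90 to 1.12 for 25% to 50% early and period hazard ratios of 0.5 to 2, narrowing to 0.94 to 1.08 for 0.67 to 1.5. It may favour drug or placebo, depending on which period carries the higher risk. The three dose arms have equal early shares, so dose-to-dose contrasts are unaffected. A reader might infer that the main efficacy conclusion is in doubt; at the design HR of 0.296 it is not. The concern is mainly for the lower doses and the dose-response model.

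**What to change.** First, report randomized counts by arm and allocation schedule. If nobody was randomized at 2:1:1:1, say so, and the point closes. Otherwise also state the expected arm sizes.

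If any subjects were randomized at 2:1:1:1, then before unblinding add allocation schedule, taken from the IRT, as follows:

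- as a stratum in the log-rank and CMH tests;
- as a term in the Cox, ANCOVA and MMRM models (SAP 9.1, 9.2.2, 9.4.2).

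Keep both existing factors, since they were used in the randomization; neither should be collapsed to make room. If strata are too sparse, adjust for schedule as a covariate in the Cox model and run the schedule-stratified log-rank as a prespecified sensitivity analysis in SAP 9.3.3. SAP 9.6 should then say whether the response rates used for MCP-Mod are adjusted for schedule.

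The cost is SAP wording and one existing variable. The downside is a slight loss of information: up to 8 strata in a comparison of about 80 subjects, or 37/8 = 4.6 flares per stratum on average for placebo plus the highest dose.
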